Day	≤21 days prior to Visit C1 (D1)	D1	D2	D3 b	D8	D15	D1	D2	D3 b	D2°	-	30 days after last dose	60 days after last dose	-
Before BNT411 infusion (on infusion days) or on day of visit	E1		X,E3, U a	X,E3, U a	X,E3	X		X,E3, U a	X,(E3) ,U a	X,E3	X,E1	X,E1	X,E1	X,E1, U a
Start of infusion			Ud											
End of infusion (+ 5 min)			X,E3		X,E3			X,E3		X,E3				
Start of infusion + 1 hour (± 5 min)			X					(X)						
Start of infusion + 2.5 hours (± 10 min)			X		X			X		X				
Start of infusion + 4 hours (± 15 min)			X		X			X		X				
Start of infusion + 6 hours (± 15 min)			X,E3ª		X			X,E3 a,		(X)				
Start of infusion + 8 hours (± 15 min)			X					(X)						

Note: Time points for blood and urine sampling are to be followed as closely as possible but time deviations no longer than 2 hours will not be reported as protocol deviations as long as the exact times of sampling and dose are known.

E1 – Single electrocardiogram (ECG) assessment.

E3 – Triplicate ECG assessments.

- X Blood sampling
- U Urine sampling

UNS - Unscheduled visit

- (X) Blood sampling will only be performed in potential additional patients enrolled to expand the cohorts for RP2D confirmation.
- (E3) Triplicate ECG assessment will only be performed in potential additional patients enrolled to expand the cohorts for RP2D.
- a Sampling time and sample volume have to be documented.
- b Time window for the Day 3 sample in the dose escalation is 24 hours  $\pm$  1 hour after the start of infusion on Day 2.
- c PK and ECG must be obtained in Cycle 3, Cycle 5, Cycle 7, and every 4 cycles thereafter (i.e., Cycles 3, 5, 7, 11, 15, etc.)
- d 6-hour urine collection after start of BNT411 infusion and total volume collected should be documented.
- e After C3D1, PBMCs (for immune phenotyping and TCR profiling) will no longer be collected. Collection of PMBCs at treatment discontinuation and/or unscheduled visits is only required if the patient discontinues trial treatment prior to C3D1.

**Table 1-5:** Overview of Safety Reporting in Different Countries

Notes: If not specified otherwise, when AE is mentioned, it should also include SAE.

Country	Trial Phase				
	Screening	Treatment Phase	Safety Follow-up Phase	Survival Follow-up Phase	Beyond Trial Closure (if patient is alive and not lost to follow-up)

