# 6.1.1 BNT411

In Part 1A, BNT411 will be administered using a 100 mL intravenous infusion on Days 1, 8 and 15 of each 3-week treatment cycle (21 days) of the first 4 cycles after all required procedures and assessments have been completed. In the following cycles thereafter, BNT411 will be administered every 3 weeks on Day 1 of each 3-week treatment cycle (21 days) after all required procedures and assessments have been completed.

In Part 1B, BNT411 will be administered using a 100 mL intravenous infusion on Days 2, 8 and 15 of each 3-week treatment cycle (21 days) of the first 4 cycles after all required procedures and assessments have been completed. In the following cycles thereafter, BNT411 will be administered every 3 weeks on Day 2 of each 3-week treatment cycle (21 days) after all required procedures and assessments have been completed.

In both Part 1A and Part 1B, patients will be administered BNT411 according to dose levels outlined in Table 4-2. BNT411 will be administered as a body weight-based dosing. A cap on dosing for patients weighing 120 kg and more will be implemented in the proposed clinical trial.

In Part 1B, for combination with atezolizumab and chemotherapy, the administration will be in the following order:

Day 1: Atezolizumab → Carboplatin → Etoposide

Day 2: **BNT411** → Etoposide

Day 3: Etoposide

For each dosing of BNT411 in Cycle 1, patients will remain in the treatment center and be closely monitored for immediate AEs for at least 6 hours. Hospitalization is required for the first 24 hours after the first BNT411 administration in Cycle 1 for clinical observation and PK sampling. Prolongation of the hospitalization beyond 24 hours may be performed at the investigator's discretion if deemed necessary based on potential risks related to the trial treatment and clinical status of the patient. For each subsequent dose of BNT411 in all cycles, patients will be monitored for at least 6 hours.

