3.1 Objectives and endpoints

Table 2: Trial design

Objectives	Endpoints
Primary	

For Parts 1 and 2: Assess safety profile	
Occurrence of Dose-Limiting Toxicities (DLTs) within a patient during the DLT evaluation periodOccurrence of treatment-emergent adverse events (TEAEs) within a patient including grade ≥ 3, serious, fatal TEAE by relationshipOccurrence of dose reduction and discontinuation of BNT411 within a patient due to TEAEs

For Part 1: Determine MTD and/or RP2D	
Maximal tolerated dose (MTD) defined as the highest tolerated doseRecommended Phase 2 dose (RP2D) based on integrated evaluation of safety, tolerability, clinical benefit, PK, and PD data, for all dose levels tested
Secondary	

For Parts 1 and 2: Establish PK profile	
PK parameters Area-under-the-concentration-time curve (AUC), clearance (CL) and volume of distribution (V_D), maximum concentration (C_{max}), time to C_{max} (T_{max}), trough concentration (C_{trough}), and terminal half-life ($T_{1/2}$)

For Part 2: Evaluate anti-tumor activity according to RECIST 1.1	
Objective response rate (ORR) defined as the proportion of patients in whom a complete response (CR) or partial response (PR) is observed as best overall response.Disease control rate (DCR) defined as the proportion of patients in whom a CR or PR or stable disease

Objectives	Endpoints
	(assessed at least 6 weeks after first dose) is observed as best overall response. 
Duration of response (DOR) defined as the time from first objective response (CR or PR) to the date of the first occurrence of objective tumor progression or death from any cause, whichever occurs first.
Exploratory	

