8.5.1 Extent of exposure

The following dose exposure variables will be derived and summarized for each treatment (BNT411 in Part 1A also BNT411, atezolizumab, carboplatin, and etoposide in Part 1B). The summaries will be based on patients in the Safety set and will be repeated for DLT evaluation set. The summary for the DLT evaluation set will be restricted to the exposure data from the first cycle (21 days).

- Number of treated cycles.
- Number of BNT411 infusions.

- Number of atezolizumab, carboplatin and etoposide infusions (Part 1B).
- (Actual)Treatment Duration (weeks) defined as follows: (Date of last administration - Date of first administration + Planned Duration) / 7, where the Planned Duration (days) is defined as the planned time between two consecutive administrations. In Part 1A, planned duration for BNT411 is one week for the first four cycles, followed by once every 3 weeks. In Part 1B, planned duration for BNT411 for the first four cycles is 6 days if the patients' last dose was the first dose within any cycle, 7 days if the patients' last dose was the second dose within any cycle and 8 days if the patients' last dose was the third dose in within any cycle. After 4 cycles planned duration for BNT411 is 3 weeks. Planned duration for atezolizumab is every 3 weeks, for carboplatin it is 21 days apart till Cycle 4 and for etoposide planned duration is one day till day 3 of the Cycle 4. Actual treatment duration is calculated for each treatment separately.
- Planned Treatment Duration (weeks) defined as (scheduled date of last administration - scheduled date of first administration + Planned Duration) / 7. The scheduled date of last administration is the date at which the last administration should be given according to the CTP schedule. Planned duration is as above.
- (Actual) Cumulative Dose defined as sum of all administered doses for each trial treatment. BNT411 (μg) for Part 1A and Part 1B and atezolizumab (mg), carboplatin (mg), and etoposide (mg) for Part 1B. Calculated for each treatment separately.
- Planned Cumulative Dose defined as sum of all planned doses, separately, for each trial treatment. BNT411 (μg) for Part 1A and Part 1B and atezolizumab (mg), carboplatin (mg), and etoposide (mg) for Part 1B.
- Dose Intensity is defined as Cumulative Dose for that trial treatment (unit for that trial treatment) / (Actual) Treatment Duration (weeks) for that trial treatment.
- RDI % (using units for BNT411) is defined as follows:

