8.6 Other analyses

8.6.1 Pharmacokinetics

Plasma and urine samples will be collected for measuring concentrations of BNT411 and its metabolites as per the schedule of timing for collection of samples for PK assessments mentioned in Table 1.3 and Table 1.4 of the CTP. For urine sampling, the exact time of sampling and the volume (mL) excreted over each collection interval must be documented. Full pharmacokinetic profiles will be documented in additional patients enrolled to confirm the RP2D. The actual date and time (24-hour clock time) of each sample will be recorded.

Plasma concentrations of BNT411 and its metabolites (if available) will be listed and summarized by cycle, day, nominal time, and cohort for each part of the trial (Part 1A and Part 1B) using descriptive statistics (n, arithmetic mean, SD, coefficient of variation [CV%], geometric mean, geometric CV%, median, minimum, and maximum) for the Full PK analysis set. The geometric CV% will be calculated as the square root of the exponentiated SD of the natural log-transformed data $\text{SQRT}(\exp(sIn^2)-1)$, where appropriate. Mean and individual plots of plasma concentrations will be presented in both the original and semi-logarithmic scales.

All PK parameters will be summarized by cohort for each part of the trial (Part 1A and Part 1B). For $T_{1/2}$, the following descriptive statistics will be calculated, if possible, n, arithmetic mean, median, CV%, SD, minimum and maximum and, for T_{max} , n, median, minimum and max will be calculated. All other PK parameters will be summarized using n, arithmetic mean, SD, CV%, geometric mean, geometric CV%, median, minimum, and maximum.

The following PK parameters will be determined from plasma concentrations of BNT411 after the first dose on Cycle 1 Day 1 (or Cycle 1 Day 2 for Part B):

- AUC_{0-24} : partial AUC from time 0 to 24 hours calculated using the linear-log trapezoidal method.
- AUC_{0-48} : partial AUC from time 0 to 48 hours calculated using the linear-log trapezoidal method.
- $AUC_{0-\text{last}}$: AUC from time 0 to the last measurable time-point calculated using the linear-log trapezoidal method.
- $AUC_{0-\tau}$: AUC from time 0 to the end of the 168-hour dosing interval (τ) calculated using the linear-log trapezoidal method.

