AUC will be computed using the linear-log trapezoidal rule. When necessary, interpolation or λ_z extrapolation may be used to estimate partial AUCs and $AUC_{0-\tau}$. The value of the extrapolated portion of any AUC ($AUC_{\% \text{extrap}}$) will be less than or equal to 20% for the AUC

to be considered well estimated. If this proportion is > 20%, then the values of AUC will be treated with caution. When AUC is calculated and listed, the AUC%_{extrap} will also be listed. Where AUC%_{extrap} >20%, AUC and all related parameters (i.e., CL, V_D) will be presented but excluded from the calculation of summary statistics. All values excluded from the summaries should be flagged in the individual listings with an explanation for the exclusion.

The λ_z will be estimated by log-linear regression of the concentration-time data associated with this phase. The decision as to which data points describe the terminal phase will be reached by inspecting the semi-logarithmic plot of the data, only considering concentrations at time points beyond T_{max}. A minimum of three data points will be used for the estimation of λ_z preferably covering a time span of at least two half-lives. Ideally, the adjusted r² value of the estimated λ_z will be > 0.80. If λ_z is poorly estimated (i.e., if a time span of at least two half-lives is not used or adjusted r² ≤ 0.80), the corresponding T_{1/2} and other parameters derived using λ_z (i.e., AUC_{0-inf}, CL, and V_D) will be flagged in the report and excluded from summaries for PK parameters dependent on λ_z .

In addition to the two plasma PK profiles collected for doses administered on Cycle 1 Day 1 (or Cycle 1 Day 2 for Part B) and Cycle 2 Day 1 (or Cycle 2 Day 2 for Part B), sparse PK samples will be collected at additional times throughout the trial (see CTP Table 1-3 and Table 1-4). Concentrations of BNT411 in pre-dose samples will be considered C_{trough} values provided they are collected between 156 and 180 hours after the start of the prior dose (i.e., 168 ± 12 hours). Concentrations of BNT411 collected within 5 minutes after the end-of-infusion will be considered end-of-infusion concentrations (C_{eoI}). Values of C_{trough} and C_{eoI} will be summarized longitudinally in tabular and graphical format by nominal elapsed time since the start of first infusion of BNT411.

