After a pre-dose void, all urine will be collected over the interval 0 to 6 hours after the start of dosing on Cycle 1 Day 1 in Part 1A and Cycle 1 Day 2 in Part 1B. Actual start and end times and total volumes of urine collections will be recorded.

The following PK parameters will be determined from urine volumes (V_u) and BNT411 concentrations (C_u) on Cycle 1 Day 1 and Cycle 2 Day 1 of Part 1A and Cycle 1 Day 2 and Cycle 2 Day 2 of Part 1B:

- Ae₀₋₆: amount of BNT411 excreted in urine over the collection interval between start and end times calculated as C_u × V_u for the interval.
- fe₀₋₆: fraction of the administered BNT411 dose excreted in urine over the collection interval between 0 and 6 hours calculated as Ae_{t1-t2}/Dose. Dose will be converted, as necessary, to reflect the amount of anhydrous BNT411 administered (molecular weight 439.5579 g/mole).
- CL_{R,0-6}: renal clearance of BNT411 over the collection interval between 0 and 6 hours calculated as Ae₀₋₆/AUC₀₋₆. Partial AUCs will be computed for plasma as described above.

Since BNT411 cannot be present in urine until after dosing, the start of the 0- to 6-hour urine collection interval will be the start of BNT411 infusion at Cycle 1 Day 1 in Part 1A or Cycle 1 Day 2 in Part 1B.

BNT411 dosing and concentration data will be combined with relevant extrinsic and intrinsic covariates and used to develop a population-based pharmacokinetic (PopPK) model suitable for subsequent simulation and exploration of exposure-response trends. The methods to be used in the development of the PopPK model, and its subsequent application, will be described in a separate Modeling and Simulation Analysis Plan (MSAP) and results reported in a separate PopPK report.

Treatment of outliers:

Individual concentration-time points, if considered anomalous, may be excluded from the analysis at the discretion of the pharmacokineticist following a review of the available documentation. Any such exclusion will be discussed with BioNTech and clearly outlined in the trial report.

Entire individual treatment profiles for a patient may be excluded following review of the available documentation and discussion with the sponsor. However, results of analysis with and without the excluded profiles may be presented in the trial report. Any such exclusion will be clearly listed in the trial report along with justification for exclusion.

Non-quantifiable concentrations:

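### SAP 8.6.1's single 156–180 h trough window does not fit Part 1B's 6-, 7- and 8-day dosing gaps, and the section asks for Cycle 2 0–6 h urine parameters with no such collection scheduled

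*SAP*

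**What the plan says.** **Trough rule.** SAP 8.6.1 treats a pre-dose concentration as Ctrough "provided they are collected between 156 and 180 hours after the start of the prior dose", which it also expresses as 168 ± 12 hours. There is no separate rule for Part 1B. Ctrough values are then to be "summarized longitudinally in tabular and graphical format by nominal elapsed time since the start of first infusion". Ctrough is one of the secondary PK parameters in SAP 3.1.

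**Dosing intervals.** Part 1A doses on Days 1, 8 and 15 of Cycles 1–4. For Part 1B, protocol 6.1.1 says that "BNT411 will be administered using a 100 mL intravenous infusion on Days 2, 8 and 15 of each 3-week treatment cycle" over the same four cycles. SAP 8.5.1 works from those gaps: in Part 1B, "planned duration for BNT411 for the first four cycles is 6 days if the" last dose given was the first of its cycle, with 7 and 8 days after the second and third. From Cycle 5 both parts dose every 3 weeks.

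**Samples.** Protocol Tables 1-3 and 1-4 schedule pre-dose blood samples through Cycles 1 and 2, and from then on "PK and ECG must be obtained in Cycle 3, Cycle 5, Cycle 7, and every 4 cycles thereafter".

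**Urine.** SAP 8.6.1 describes one 0–6 h collection, with the first BNT411 dose (Cycle 1 Day 1 in Part 1A, Cycle 1 Day 2 in Part 1B). The next sentence asks for Ae0-6, fe0-6 and CLR,0-6 in Cycle 2 as well.

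**The concern.** A trough is the concentration at the end of a dosing interval, and protocol 8.9 describes Ctrough as a pre-dose trough concentration. A window fixed at 168 h identifies it only where the interval is 168 h. That holds throughout the weekly phase of Part 1A, but in Part 1B only for the Day 8 to Day 15 gap. So SAP 8.6.1 and SAP 8.5.1 do not describe the same dosing schedule. At stake is the Part 1B display of a named secondary parameter, which would be nearly empty if visits run to time.

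The urine request is a contradiction within one section. Followed literally, it leaves three promised parameters per part without values and without explanation.

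**Working it through.** **1. The SAP's own figure.** 168 − 12 = 156 h and 168 + 12 = 180 h, which reproduces the stated window.

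**2. Nominal gaps.** Number the trial days as (cycle − 1) × 21 + day. Gap = (day of this dose − day of the prior dose) × 24 h. The first pre-dose sample is left out because it has no prior dose.

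| Pre-dose sample | Part 1A gap | In window | Part 1B gap | In window |
|---|---|---|---|---|
| Cycle 1 Day 8 | (8 − 1) × 24 = 168 h | yes | (8 − 2) × 24 = 144 h | no |
| Cycle 1 Day 15 | (15 − 8) × 24 = 168 h | yes | (15 − 8) × 24 = 168 h | yes |
| Cycle 2, first dose | (22 − 15) × 24 = 168 h | yes | (23 − 15) × 24 = 192 h | no |
| Cycle 3, first dose | (43 − 36) × 24 = 168 h | yes | (44 − 36) × 24 = 192 h | no |
| Cycle 5, first dose (after Cycle 4 Day 15) | (85 − 78) × 24 = 168 h | yes | (86 − 78) × 24 = 192 h | no |
| Cycle 7 onward | 21 × 24 = 504 h | no | 504 h | no |

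For samples that follow a weekly-phase dose, Part 1A has 5 of 5 and Part 1B has 1 of 5. Leaving out Cycle 5 gives 4 of 4 and 1 of 4.

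**3. With the tolerance tied to the scheduled interval.** The windows become 132–156 h, 156–180 h and 180–204 h. Part 1B then has 5 of 5 at nominal times, and Part 1A stays at 5 of 5.

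**4. Visit windows (illustration only).** Protocol Table 1-2 allows ±1 day at Days 8 and 15 and ±3 days at Day 1. In whole-day shifts, the Part 1B Cycle 1 Day 8 sample enters the current window only if its gap is one day longer than nominal (144 + 24 = 168 h). The Day 2 samples of Cycles 2, 3 and 5 enter only if theirs is one day shorter (192 − 24 = 168 h).

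Assume that each cycle is anchored on its own Day 1, that Day 2 has no window, and that a visit falls on its nominal day with probability q, the rest spread evenly over the permitted days. The documents give no value for q. At q = 0.8 in Part 1B:

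- Current rule: Cycle 1 Day 8 0.10; Cycle 1 Day 15 0.8² + 2 × 0.1² = 0.66; each of the three Day 2 samples 0.8 × (0.2/6) + 0.1 × 0.8 + 0.1 × (0.2/6) = 0.11. Sum = 0.10 + 0.66 + 3 × 0.11 = 1.09 of 5.
- Scheduled-interval rule: 0.80 + 0.66 + 3 × [0.8² + 2 × 0.1 × (0.2/6)] = 0.80 + 0.66 + 3 × 0.647 = 3.40 of 5.

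| Probability of the nominal day | Current rule | Scheduled-interval rule |
|---|---|---|
| 0.9 | 1.05 | 4.15 |
| 0.8 | 1.09 | 3.40 |
| 0.6 | 1.16 | 2.20 |
| all permitted days equally likely | 1.10 | 1.10 |

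The last column also equals Part 1A under the current rule. The gain therefore runs from about 3 samples down to none.

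**5. Urine.** Ae0-6 is urine concentration times urine volume over the interval, and fe0-6 and CLR,0-6 are built on it. SAP 8.6.1, protocol 8.9 (total volume on Cycle 1 Day 1) and footnote d of Tables 1-3 and 1-4 (attached only to the Cycle 1 start-of-infusion cell) all place the timed collection at the first dose. Cycle 2 has only urine samples in the row for pre-infusion or day-of-visit sampling. Timed Cycle 2 collections: 0. Cycle 2 parameters requested: 3 per part. Obtainable: 0 of 3.

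**The case against.** The best defence is that 168 ± 12 h is deliberate. SAP 8.6.1 uses one 168 h dosing interval for AUC in both parts, and a common window keeps Ctrough comparable between them. On that view, the off-schedule samples it admits, with actual gaps near 168 h, are the right ones. The SAP gives no such reason, however, and the rule removes on-schedule samples of a planned endpoint. What stands is that a scheduled-interval rule puts 144, 168 and 192 h values into one longitudinal display, where differences in interval could look like a trend over time. The display must therefore show the interval.

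It is also fair that little is lost in practice. SAP 8.6.1 says that plasma concentrations "will be listed and summarized by cycle, day, nominal time, and cohort", and for the population PK model "BNT411 dosing and concentration data will be combined with relevant extrinsic and intrinsic covariates". SAP Table 4 lists only two Part 1B cohorts, sized at three to six DLT-evaluable patients before any backfilling. Summary statistics also require at least two thirds of values to be quantifiable, and neither the assay limit nor a human half-life is given, so a corrected table could still be thin. All of this limits the impact without justifying the window.

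On urine, the sample-volume footnote also appears at the Cycle 2 six-hour ECG cell in Tables 1-3 and 1-4, which might hint at an intended collection. That cell carries no urine code, and the text in both documents points to Cycle 1 only. The mismatch stands, but it should be resolved against the schedule.

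**Conclusion.** Both points hold. At nominal times, 1 of 5 Part 1B pre-dose samples after a weekly-phase dose counts as Ctrough, against 5 of 5 in Part 1A. The Cycle 2 0–6 h urine parameters cannot be produced in either part. The counts rest only on the documented schedule; the visit-window figures rest on assumed probabilities and are illustrative. The impact is minor and descriptive.

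Three stronger readings are not supported:

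- *Part 1B trough data are lost.* They are not; they drop out of the Ctrough table and figure only.
- *The correction recovers four samples per patient.* That is the nominal-time result. With the permitted visit shifts the expected gain is smaller, and it is nil if all permitted days are equally likely.
- *The 168 h interval used for AUC, accumulation ratio and effective half-life must change, or needs a Part 1B caveat.* The mean Part 1B interval is (144 + 168 + 192)/3 = 168 h. Cycle 2 sampling after the first dose stops at 24 h in Part 1B and 48 h in Part 1A, leaving 144 h and 120 h unsampled, so reliance on extrapolation is not peculiar to Part 1B. SAP 8.6.1 already has an extrapolation rule.

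**What to change.** In SAP 8.6.1:

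1. Define Ctrough as a pre-dose sample taken within ±12 h of the interval scheduled before that dose. For Part 1A this is 168 h through Cycle 5 Day 1. For Part 1B it is 144 h at Day 8, 168 h at Day 15, and 192 h at Day 2 of Cycles 2–5.
2. Show the nominal interval in the Ctrough table and figure.
3. Report the 504 h pre-dose samples (Cycle 7 onward) separately, in both parts.
4. Reconcile the urine-parameter sentence with the sampling schedule by removing the Cycle 2 days from it.

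A permitted one-day shift would still fall outside ±12 h, as it does now in Part 1A; the change puts the two parts on the same footing. The cost is SAP wording and the matching table programming. No new samples are needed.

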All concentration values reported as no results (not collected or not determined) values will be treated as missing. For the calculation of concentration summaries, all concentrations below the quantifiable limit (BLQ) will be treated as 0. For the purpose of calculating PK parameters and plotting mean and individual concentration-time profiles, BLQ values will be treated as 0 prior to the first measurable concentration. After the first measurable concentration, subsequent BLQ values within the PK profile will be treated as missing. Descriptive statistics at any point will only be calculated if at least 2/3 of the individual data were measured and were quantifiable.

Dose-proportionality analysis:

The dose-proportionality of the PK parameters $AUC_{0-\text{last}}$, $AUC_{0-\text{inf}}$, and C_{\max} for the single-dose PK profile and $AUC_{0-\tau}$ and C_{\max} for the multiple-dose PK profile will be investigated over the administered dose range using the following power model,

$\ln(\text{parameter}) = a + b * \ln(\text{dose})$, where a is the intercept and b is the slope.

Dose proportionality will be assessed for Cycle 1 Day 1 (or Cycle 1 Day 2 for Part B) and Cycle 2 Day 1 (or Cycle 2 Day 2 for Part B) of the trial separately.

Each log-transformed PK parameter will be fit with a power model with a fixed effect term for log-transformed dose. For each PK parameter, the slope and associated 90% CI will be presented. Dose proportionality will be assessed based on whether the 90% CI includes 1.0.

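### After the first measurable concentration, BLQ values count as 0 in the concentration tables but are dropped from the mean plots (gap up to 50%), and the zeros leave geometric statistics at 0 or undefined at partly BLQ time points

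*SAP*

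**What the plan says.** All the relevant text is in SAP 8.6.1.

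- **Tables.** "For the calculation of concentration summaries, all concentrations below the quantifiable limit (BLQ) will be treated as 0". No time restriction is attached.
- **PK parameters and plots (mean and individual).** "BLQ values will be treated as 0 prior to the first measurable concentration". Then: "After the first measurable concentration, subsequent BLQ values within the PK profile will be treated as missing".
- **Threshold.** "Descriptive statistics at any point will only be calculated if at least 2/3 of the individual data were measured and were quantifiable".
- **Statistics planned for concentrations.** By cycle, day, nominal time and cohort, the list includes "geometric mean, geometric CV%, median, minimum, and maximum) for the Full PK analysis set". The geometric CV% rests on logs: "The geometric CV% will be calculated as the square root of the exponentiated SD of the natural log-transformed data". The qualifier that follows this formula limits it to suitable cases without saying which those are.
- **Figures.** "Mean and individual plots of plasma concentrations will be presented in both the original and semi-logarithmic scales".

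No other section reconciles the table rule with the plot rule, asks for the number of BLQ values per time point, or says how zeros enter the geometric statistics.

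**The concern.** The same samples, at the same nominal time and in the same cohort, produce two different means in one report, one in the table and one in the figure. A reader comparing them would find the plotted means above the tabulated ones wherever some patients have fallen below the limit, with no note to explain it.

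The second problem is computational. A programmer who follows the table rule literally feeds zeros into log-based statistics. The output is then 0, an error or a blank, and whoever programs it must choose a remedy (drop, substitute or suppress) once the data are in hand.

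The PK profile is a secondary objective for Part 1, and the SAP plans no efficacy analysis there, so the concentration tables and figures are a visible part of the report.

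**Working it through.** The plan states no figure for a table-to-plot difference, so there is nothing of its own to reproduce.

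**Inputs**

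- BLQ = 0 in tables; BLQ = 0 in plots before, and missing after, the first measurable concentration (SAP 8.6.1).
- At least 2/3 of values quantifiable for any descriptive statistic (SAP 8.6.1).
- Three to six DLT-evaluable patients per cohort (SAP 6), up to 14 with backfill (Protocol 4.1.1.1); the first three dose levels start as single-patient cohorts.

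**Step 1: arithmetic means.** At one time point let N values be measured, q of them quantifiable with mean m, and the other N − q be BLQ after the first measurable concentration.

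- Table mean = (q·m + (N − q)·0)/N = q·m/N.
- Plotted mean = q·m/q = m.
- Ratio, plot to table = N/q.

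The threshold requires q/N ≥ 2/3, so N/q ≤ 3/2 = 1.5.

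| N | Most BLQ allowed | Smallest q | Largest N/q | Plot above table |
|---|---|---|---|---|
| 1 or 2 | 0 | N | 1.00 | 0% |
| 3 | 1 | 2 | 3/2 = 1.50 | 50.0% |
| 4 | 1 | 3 | 4/3 = 1.33 | 33.3% |
| 5 | 1 | 4 | 5/4 = 1.25 | 25.0% |
| 6 | 2 | 4 | 6/4 = 1.50 | 50.0% |
| 14 | 4 | 10 | 14/10 = 1.40 | 40.0% |

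The ceiling is reached only at exactly one third BLQ (N = 3, 6, 9 or 12). With one BLQ value in six, the ratio is 6/5 = 1.2. Taking the plotted mean as the base, the 50% excess becomes a shortfall of 1 − 2/3 = 33.3%. Counting uncollected samples in or out of the denominator leaves the maximum at 1.5.

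**Step 2: geometric statistics.** The geometric mean is exp(mean of ln x). Take the illustrative values 1, 2 and BLQ, which pass the threshold (2 of 3 quantifiable).

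- BLQ = 0: ln(0) does not exist. In product form the geometric mean is (1·2·0)^(1/3) = 0. The SD of the logs, and so the geometric CV%, is undefined.
- Quantifiable values only: √(1·2) = 1.41.
- Arithmetic means of the same data: table (1 + 2 + 0)/3 = 1.0; plot (1 + 2)/2 = 1.5.

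With no BLQ value there is no difficulty: 1, 1.5 and 2 give 3^(1/3) = 1.44.

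**Step 3: where it applies.**

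| Time point | Table against plot | Geometric statistics |
|---|---|---|
| No BLQ | agree | computable |
| Some BLQ, up to 1/3, before first measurable concentration | agree (both 0) | 0 or undefined |
| Some BLQ, up to 1/3, after it | ratio N/q, up to 1.5 | 0 or undefined |
| More than 1/3 BLQ | no tabulated mean | not calculated |

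**Step 4: the median.** BLQ values, whether set to 0 or LLOQ/2, take the lowest ranks, at most N/3 of them. The median uses ranks from N/2 upward (the 2nd value of 3; the 3rd and 4th of 6), which are quantifiable. It is therefore the same under either substitution.

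**The case against.** The strongest reply has four parts.

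**Separate rules can be deliberate.** They are prespecified openly, and zeros cannot be drawn on the semi-logarithmic plots the SAP requires. This stands for individual profiles. It does not cover mean plots: a mean of q·m/N with q ≥ 2N/3 is positive and can be drawn on a log axis.

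**The reach is narrow.** This stands. A reader might infer that the planned geometric means are lost altogether. They are not: only concentration summaries at time points with some, but no more than one third, BLQ values are affected. Cmax and AUC follow the parameter rule, and dose proportionality is fitted to those. A reader might also infer that plots always drop BLQ values; before the first measurable concentration they use 0, as the tables do.

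**Low-dose cohorts.** It is tempting to say the conflict is worst there. The design does not support this: the first three dose levels are single-patient unless expanded, and with N = 1 or 2 the threshold allows no BLQ value in a summary.

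**Little depends on it.** No hypothesis is tested, escalation rests on DLT counts with PK considered if available, concentrations are listed, and population PK has its own plan. This stands and keeps the point minor. It does not answer the geometric problem, where following the stated rule gives an unusable result. The qualifier after the CV% formula softens that slightly, but it is not attached to the geometric mean and gives no rule for zeros.

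**Conclusion.** The point holds within limits. After the first measurable concentration, table and plot means disagree at any summarised time point with a BLQ value, by a factor of N/q. At the same kind of time point, and also at a partly BLQ one before the first measurable concentration, the geometric mean and geometric CV% are 0 or undefined.

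The 50% is a ceiling, not an expected difference. It needs exactly one third BLQ, although in a cohort of three a single BLQ value is enough. The documents give neither the quantification limit nor any BLQ frequency, so nothing can be said about how many time points will be affected, or that readers will be misled about the PK profile as a whole.

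The result assumes that the two-thirds threshold governs plotted means as well as tabulated ones. If it does not, figures could show means where tables have none, but where both exist the gap is still at most 50%. It is a minor point, worth correcting because it is cheap and removes a choice otherwise made after the data are seen.

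**What to change.** In the paragraph of SAP 8.6.1 on non-quantifiable concentrations:

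1. State that mean plots show the same mean as the table. Keep the rule of 0 before and missing after the first measurable concentration for individual profiles and PK parameter derivation only. The ratio of plotted to tabulated mean then becomes 1.00.
2. Show the number of BLQ values at each time point in the table, with a footnote to the figure.
3. For geometric concentration statistics at a time point with any BLQ value, choose one rule in advance: substitute LLOQ/2 and flag it, or report them as not calculable and rely on the median, which is already planned and unchanged by the choice between 0 and LLOQ/2.

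The cost is a few SAP sentences, a small amount of extra programming and some footnotes. No new data are needed.
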